Appendix Table 2: ICD-10 codes for identifying maternal venous thromboembolism

ICD-10	Condition
I26.0	Pulmonary embolism with mention of acute cor pulmonale
I26.9	Pulmonary embolism without mention of acute cor pulmonale
I80.1	Phlebitis and thrombophlebitis of femoral vein
I80.2	Phlebitis and thrombophlebitis of other deep vessels of lower extremities
I80.3	Phlebitis and thrombophlebitis of lower extremities, unspecified
O08.2	Embolism following abortion and ectopic and molar pregnancy
O22.3	Deep thrombophlebitis in pregnancy
O87.1	Deep phlebothrombosis in the puerperium
O88.2	Obstetric blood-clot embolism
I80.8	Phlebitis and thrombophlebitis of other sites
I80.9	Phlebitis and thrombophlebitis of unspecified site
I81	Portal vein thrombosis
I82.0	Budd Chiari syndrome
I82.1	Thrombophlebitis migrans
I82.2	Embolism and thrombosis of vena cava
I82.3	Embolism and thrombosis of renal vein
I82.8	Embolism and thrombosis of other specified veins
I82.9	Embolism and thrombosis of unspecified vein
O22.9	Venous complication in pregnancy, unspecified
O87.9	Venous complication in the puerperium, unspecified
G08	Intracranial and intraspinal phlebitis and thrombophlebitis
I63.6	Cerebral infarction due to cerebral venous thrombosis, nonpyogenic
I67.6	Nonpyogenic thrombosis of intracranial venous system
O22.5	Cerebral venous thrombosis in pregnancy
O87.3	Cerebral venous thrombosis in the puerperium
Considered but not included	
G95.1	Vascular myelopathies
H34.8	Other retinal vascular occlusions
I51.3	Intracardiac thrombosis, not elsewhere classified
I80.0	Phlebitis and thrombophlebitis of superficial vessels of lower extremities
K55.0	Acute vascular disorders of intestine
K64.5	Perianal venous thrombosis
K75.1	Phlebitis of portal vein
O22.2	Superficial thrombophlebitis in pregnancy
O22.8	Other venous complications in pregnancy
O69.5	Labour and delivery complicated by vascular lesion of cord
O87.0	Superficial thrombophlebitis in the puerperium
O87.8	Other venous complications in the puerperium
T80.1	Vascular complications following infusion, transfusion and therapeutic injection

Appendix Table 3: ICD-10 codes for identifying hypertensive disorders of pregnancy

ICD-10	Condition
O11	Pre-eclampsia superimposed on chronic hypertension
O13	Gestational [pregnancy-induced] hypertension
O14.0	Mild to moderate pre-eclampsia
O14.1	Severe pre-eclampsia
O14.2	HELLP syndrome
O14.9	Pre-eclampsia, unspecified
O15.0	Eclampsia in pregnancy
O15.1	Eclampsia in labour
O15.2	Eclampsia in the puerperium
O15.9	Eclampsia, unspecified as to time period
Considered but not included for this category	
O10	Pre-existing hypertension complicating pregnancy, childbirth and the puerperium
O12	Gestational [pregnancy-induced] oedema and proteinuria without hypertension
O16	Unspecified maternal hypertension

SMR01 and SMR02 records with a relevant date of admission and any relevant ICD10 code recorded against main condition or any other condition will be used to identify admissions for the above 3 conditions. All SMR02 record types will be included (i.e. antenatal, delivery, and postpartum admissions).

Appendix 2: Rationale for selection of pregnancy-related outcome measures to be used in COPS study to assess impact of COVID-19 infection and safety of COVID-19 vaccination

A list of outcomes to be examined post-infection was drawn up in May 2020 for the initial COPS protocol document, based on what was known about COVID-19 at that point. A provisional list of outcomes to be examined post-vaccination (as part of vaccine safety monitoring) was drawn up in April 2021, based on a review of the following sources conducted up to 12 Feb 2021.

- MHRA public assessment record for the Pfizer vaccine (released at the time the MHRA first gave approval for use on 2 Dec 2020) - <https://www.gov.uk/government/publications/regulatory-approval-of-pfizer-biontech-vaccine-for-covid-19>
- MHRA public assessment record for the Oxford vaccine (released at the time the MHRA first gave approval for use on 30 Dec 2020) - <https://www.gov.uk/government/publications/regulatory-approval-of-covid-19-vaccine-astrazeneca>. No public assessment records for other vaccine types available at the time of review
- Data from the MHRA on possible adverse events reported through the Yellow Card scheme up to 31 Jan 2021. <https://www.gov.uk/government/publications/coronavirus-covid-19-vaccine-adverse-reactions>

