Pregnant women will be identified through the COPS² study database if they appear on one or more of the data sources listed for the identification of pregnant women in Table 1.

Table 1: Overview of data sources used for analysis

Data	Data source

Datasets required to identify pregnant women in the general population and associated pregnancy start and end dates:
	
 • New national data return developed as part of the response to the COVID-19 pandemic providing information on women booking for antenatal care with NHS maternity services: for identification of women with ongoing pregnancies in near real-time (all other records that identify end of pregnancy events) • GP consultation data: for identification of women with early miscarriage or ectopic pregnancy not managed in hospitals • Scottish Morbidity Record (SMR) 01: for identification of women with early miscarriage or ectopic pregnancy managed in hospitals • Termination of pregnancy statutory notifications (AAS records) • SMR 02: for identification of later miscarriage, stillbirth, and live births managed in hospital (and some home births) • National Records of Scotland (NRS) statutory stillbirth registrations • National Records of Scotland (NRS) statutory live birth registrations • New national data return developed as part of the response to the COVID-19 pandemic providing information on live births notified by maternity services to NHS Board child health administrative departments: for near real-time access to data that allows intergenerational linkage of records relating to mothers and their babies. 
Note that this is already established as part of the COPS study and methodology is set out in the Protocol for estimating the number of COVID-19 vaccinations delivered to pregnant women in Scotland and for describing the uptake and coverage of vaccination in the pregnant population.

Datasets required to identify characteristics of pregnant population
	
 • Covariates of interest include: Maternal age, deprivation score, urban/rurality score, ethnicity, pre-pregnancy clinical vulnerability exc diabetes, diabetes, BMI, smoking status, and linked PCR test data to capture confirmed cases of COVID-19 infection. 
Note that all are available through the COPS study database.

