
Datasets required to identify vaccinated individuals
	
 • Data from the National Clinical Data Store (NCDS). Information recorded on the National Vaccine Management Tool (VMT) and GPIT system (Primary care practice medical record database) flows to the

² Stock SJ, McAllister D, Vasileiou E, *et al.* COVID-19 in Pregnancy in Scotland (COPS): protocol for an observational study using linked Scottish national data. *BMJ Open* 2020;**10**:e042813. doi: 10.1136/bmjopen-2020-042813. Available from: [COVID-19 in Pregnancy in Scotland \(COPS\): protocol for an observational study using linked Scottish national data | BMJ Open](#)

	NCDS, from where it is cleaned and then linked to the COPS data. Relevant data of interest: vaccination date, type, dose.
Datasets required to identify outcomes of interest	
 Data from a number of sources that hold pregnancy, maternal and neonatal outcome data will be brought into the COPS study dataset. Sources include: SMR01, SMR02, national linked anomaly database, SICSAG critical care admissions, NRS deaths.

3.5: Study Variables

3.5.1: Study Outcomes

Maternal, pregnancy and neonatal outcomes of interest are listed in Table 2. In our main analyses, we will assess the risk of each outcome in vaccinated women and their unvaccinated controls (i.e. classifying each woman as having the outcome or not), and will not attempt to capture any differences between the groups in the time to these events. As noted in Table 2, there are different periods of risk for each outcome (referred to as “outcome-specific follow-up period” throughout this protocol). For example, women will be considered at risk of any miscarriage from conception up to 23⁺⁶ weeks gestation, and at risk for stillbirth from 24⁺⁰ weeks gestation to the end of pregnancy. Women without an observed outcome who had not completed follow-up to the end of the follow-up period for a specific outcome in either the pre-pandemic (i.e. outcome-specific follow-up period not completed before 01 March 2020) or in the pandemic time period (i.e. outcome-specific follow-up period not completed before date of data extraction) will not be eligible for inclusion in the analysis for that outcome.

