Outcomes have been aligned as far as possible with the relevant Brighton/GAIA outcome definitions, and also agreed with those in the MHRA / four nations working group on COVID-19 vaccination in pregnancy and comply with those recommended by the WHO³. See Appendix 2 for full rational and sources of information behind included outcomes, definitions, timings etc. as presented in Table 2.

Both primary and secondary outcomes are of interest, with the former being a composite measure including the associated secondary outcomes, and the latter being a narrower measure or subset of the associated primary outcome, e.g. primary outcome = small for gestational age, secondary outcome = very small for gestational age.

Venous thromboembolism in pregnancy is a standard maternal outcome that may be influenced by infection or vaccination and is not the same as vaccine associated thrombosis with thrombocytopenia (VATT), the condition associated with the AstraZeneca vaccine⁴. Similarly, the pregnancy related bleeding outcome includes disseminated intravascular coagulation (DIC) which can occur in association with massive obstetric haemorrhage: again, this is distinct from VATT. Full lists of ICD10 codes used to identify the maternal outcomes venous thromboembolism, pregnancy-related bleeding, and hypertensive disorders of pregnancy are shown in Appendix 1.

³ <https://www.who.int/publications/m/item/safety-surveillance-of-covid-19-vaccines-in-pregnant-and-breastfeeding-women>

⁴ Pavord, S et al (2021). Clinical Features of Vaccine-Induced Immune Thrombocytopenia and Thrombosis. NEJM. DOI: 10.1056/NEJMoa2109908

'Clean windows' will be applied to outcomes, where appropriate, so that only new or incident cases occurring post vaccination will be counted. Specifically, a clean window of the current pregnancy will be applied for the venous thromboembolism, pregnancy-related bleeding, and hypertensive disorders of pregnancy outcomes (i.e. women will only be included if there is no prior record of these outcomes in the current pregnancy). See Table 2. For both congenital anomalies and pregnancy-related bleeding, further descriptive analyses will be conducted looking at more specific diagnoses within these broader outcome groups if we find evidence for an association between vaccination and these outcomes. For example, for pregnancy-related bleeding, we can further disaggregate into early pregnancy bleeding, obstetric haemorrhage, and DIC.

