Longer term child outcomes, including immune function and infection, and neurodevelopment, will be addressed in future work as required.

Other adverse outcomes that are not specific to pregnant women, will be investigated separately for the whole population as part of wider adverse events monitoring in Scotland. If these analyses suggest any signals in the pregnant population, those outcomes would be investigated in the pregnant population using the COPS data infrastructure, as required.

Table 2: Maternal, pregnancy and neonatal outcome measures for monitoring of safety of COVID-19 vaccination in pregnancy

Outcome measure	Definition	Primary or secondary outcome?	Clean window requirement to identify incident cases	Timing of vaccination to be included	Post vaccination risk period to be examined	Estimated background risk of outcome (%)
Maternal outcomes						
Hypertensive disorders of pregnancy	See ICD10 code list. Note that hypertensive disorders can only be diagnosed at >20 weeks.	Primary	No prior record in this pregnancy	Any	Up to E plus PP	10.0
Venous thromboembolism	See ICD10 code list	Primary	No prior record in this pregnancy	Any	Up to E plus PP	0.15
Pregnancy-related bleeding	See ICD10 code list	Primary	No prior record in this pregnancy	Any	Up to E plus PP	30.0 (for postpartum haemorrhage)
ICU admission or death (any cause)	ICU admission as identified on SICSAG record Death from any cause	Primary	None (but exploration to be undertaken of reasons for any pre-vaccination ICU admission where these are documented)	Any	Up to E plus PP	Unknown
Pregnancy outcomes						
Miscarriage	Miscarriage at <24 completed weeks gestation	Primary	None	Up to 23w+6d gestation	Up to 23+6 gestation	10.0 – 20.0

• First trimester miscarriage	Miscarriage at <14 completed weeks gestation	Secondary	None	Up to 13+6 gestation	Up to 13+6 gestation	Unknown
• Second trimester miscarriage	Miscarriage at 14-<24 completed weeks gestation	Secondary	None	Up to 23+6 gestation	14+0 to 23+6 gestation	Unknown
Ectopic pregnancy	Ectopic pregnancy ending at any gestation	Primary	None	Up to 2+6 gestation	Up to E	1.0
Stillbirth	Spontaneous fetal loss at ≥24 completed weeks gestation Any cause of fetal death Losses related to termination of pregnancy excluded	Primary	None	Any	24+0 to E	0.4
Baby outcomes (live births only unless otherwise stated)						

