In addition, vaccinated pregnant women will also be matched by season of conception (quarter) to historical controls from the pandemic and pre-pandemic periods due to the seasonality of some outcomes. It is not necessary to do this for contemporary controls (from the pandemic vaccination period) as those pairs will be matched by calendar date (i.e. matching a vaccinated woman by maternal and gestational age, on the day of vaccination to a control of the same maternal and gestation age, on the same date).

For comparisons between vaccinated and unvaccinated matched individuals, the index date (reference point for matching maternal and gestational age, and season of gestation for analyses involving controls from historical periods only) will be the date of vaccination.

⁵ Donegan K, King B, Bryan P. Safety of pertussis vaccination in pregnant women in UK: observational study BMJ 2014; 349:g4219 doi:10.1136/bmj.g4219. Available from: <https://www.bmj.com/content/349/bmj.g4219>

The matching strategy for each of the three analyses is shown in Table 5.

Table 5: Matching strategy for each analysis of the matched cohort study

Analysis	Time period for control group*	Matched three controls to each case by:	Notes
Primary analysis	Pre-pandemic period (01 January 2015 to 29 February 2020)	
 Maternal age Gestational age Season of conception (quarter) 	
 Aim to match to three unvaccinated controls Maternal age matched by ± 1 year but relaxed at tails of maternal age distribution Gestational age matched by same week but relaxed at tails of the gestation distribution
Supplementary analysis 1	Pandemic vaccination period (from 08 December 2020 to date of data extraction), excluding cases and controls with confirmed COVID-19 between six weeks preconception to end of outcome-specific follow-up period	
 Maternal age Gestational age 	
Supplementary analysis 2	Pandemic vaccination period (from 08 December 2020 to date of data extraction), including cases and controls with confirmed COVID-19 between six weeks preconception to end of outcome-specific follow-up period	
 Maternal age Gestational age 	

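### For hypertensive disorders, the clean window cannot exclude disease diagnosed after 20 weeks but before vaccination without an admission, so for later vaccination some counted cases may not be new

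*Protocol*

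**What the plan says.** Section 3.5.1 gives the purpose of the clean windows as "so that only new or incident cases occurring post vaccination will be counted". The rule for venous thromboembolism, pregnancy-related bleeding and hypertensive disorders is that "women will only be included if there is no prior record of these outcomes in the current pregnancy".

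What counts as a record of a hypertensive disorder is fixed in Appendix 1, below Appendix Table 3: "SMR01 and SMR02 records with a relevant date of admission and any relevant ICD10 code recorded against main condition or any other condition". Antenatal, delivery and postpartum SMR02 records all qualify. Table 1 describes the outcome sources thus: "Sources include: SMR01, SMR02, national linked anomaly database, SICSAG critical care admissions, NRS deaths". Its entry for primary care is limited to finding pregnancies: "GP consultation data: for identification of women with early miscarriage or ectopic pregnancy not managed in hospitals". No onset or diagnosis date separate from the admission date is defined.

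Table 2 admits vaccination at any time from six weeks before conception to the end of pregnancy for this outcome, with follow-up to the end of the postpartum period and a background risk of 10.0%. Its definition column adds: "Note that hypertensive disorders can only be diagnosed at >20 weeks".

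In section 3.6 the index date is the date of vaccination, described as the "reference point for matching maternal and gestational age, and season of gestation for analyses involving controls from historical periods only". Section 3.5.3 names pregnancy-induced hypertension as a pregnancy complication. It promises additional analyses where differential uptake among women with complications might explain an association, but only once a signal has been seen.

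**The concern.** The stated aim is to count incident cases only. The tool is the absence of an earlier hospital record, and that is weaker than the absence of earlier disease.

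Take a woman found to have gestational hypertension at a clinic at 30 weeks and not admitted. She is vaccinated at 33 weeks, and O13 (on the code list) is recorded at her delivery admission at 39 weeks. She passes the clean window and enters the analysis as a new case after vaccination, although the disease came first.

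Two consequences follow:

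- **Dilution.** Disease that predates vaccination cannot be caused by it. If it leaks equally into both groups, the estimate moves toward the null, which is the less safe direction for a safety study.
- **Selection.** If existing hypertension makes a woman more or less likely to be vaccinated, prior disease will be more or less frequent among the vaccinated than among pre-pandemic controls, who were never selected by uptake. The bias can then go either way.

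Hypertensive disorders fall in the frequent-outcome class of Table 6, so the study will tend to read this estimate as informative even when the effect is modest.

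**Working it through.** **1. Does the leak follow from the text?**

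- A case exists only if an SMR01 or SMR02 record carries a listed code, and it is dated by admission (Appendix 1).
- The clean window removes a woman only if such a record already exists in this pregnancy (section 3.5.1).
- The outcome sources in Table 1 are worded as included rather than as a complete list, but Appendix 1 settles the source for this outcome.
- Disease diagnosed without an admission therefore cannot trigger the clean window. It first appears at a later admission, often the delivery.
- By Table 2's note, prior disease can exist only after 20 weeks, so earlier index dates are free of the problem.

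**2. Does a planned analysis catch it?** The subgroups are by dose number, class and type. The sensitivity analyses drop preconception vaccination, drop known multiples, or separate controls vaccinated more than six weeks before conception. The supplementary analyses change the controls and keep the outcome rule. None restricts by gestation at vaccination.

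**3. The plan's nearest figure.** Table 6 gives 94% power for a 10% risk, relative risk (RR) 1.2, 5,000 v 15,000. A pooled two-proportion test at two-sided 0.05 (the protocol does not state sidedness) gives:

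- 10% in the vaccinated v 10%/1.2 = 8.33% in controls: 94.4%, which reproduces the table.
- 12% in the vaccinated v 10% in controls, reading the Table 2 background risk as the control risk: 97.5%.

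**4. Size, under assumptions.** The documents do not give how many events follow late vaccination, what share of those were already present, or how uptake depends on hypertension. I assume that half the events follow an index date after 20 weeks and that 10–40% of those are prior disease. The share of all counted events that is prior disease is then s = 0.5 × 0.10 = 0.05 to 0.5 × 0.40 = 0.20.

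*Equal leakage, true RR 1.2.* Observed RR = 1 + (1.2 − 1)(1 − s).

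| s | Observed RR | Power, 10% control risk | Power, 8.33% control risk |
|---|---|---|---|
| 0 | 1.20 | 97.5% | 94.4% |
| 0.05 | 1 + 0.2 × 0.95 = 1.19 | 96.2% | 92.2% |
| 0.20 | 1 + 0.2 × 0.80 = 1.16 | 88.7% | 81.9% |

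Both power columns are for 5,000 v 15,000.

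*No true effect, unequal leakage.* Let k be the frequency of prior disease in the vaccinated relative to controls (roughly the uptake ratio). Observed RR = 1 + s(k − 1). With a 20% share among late events, s = 0.5 × 0.20 = 0.10. With k = 1.5, RR = 1 + 0.10 × 0.5 = 1.05, that is 10.5% v 10%.

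- Pooled risk = (0.105 × 5,000 + 0.10 × 15,000)/20,000 = 0.10125.
- At 5,000 v 15,000: standard error = √[0.10125 × 0.89875 × (1/5,000 + 1/15,000)] = 0.00493; z = 0.005/0.00493 = 1.0.
- At 10,000 v 30,000: standard error 0.00348; z = 1.4.
- With k = 0.5 the RR is 0.95, and z is about −1.0 and −1.5.

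All of these z values are before any multiplicity correction.

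**The case against.** The strongest reply is that the effect is small and partly guarded against.

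- **Controls leak too.** The clean-window wording covers women generally, and controls are matched on gestational age at the index date. This stands: equal leakage only attenuates, and a spurious association needs differential uptake.
- **Adjustment and multiplicity.** The adjusted model includes BMI, diabetes and clinical vulnerability, which may absorb part of any uptake difference. Section 4.4 also plans a multiplicity correction. Both stand.
- **Section 3.5.3 already promises further work.** This stands in part. It addresses differential uptake, but only after a signal, so it cannot help with a diluted null or with apparent protection that hides harm.
- **Timing plots are planned.** Section 4.3 describes time from vaccination or matching to outcome, but for this outcome those dates are the same admission dates.

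A reader might infer that the plan will produce a false safety signal. The documents do not support that. If the 20% share and k = 1.5 are applied to the whole cohort, RR is 1.10, with z = 2.0 at 5,000 v 15,000 and 2.9 at 10,000 v 30,000. That treats every woman as vaccinated after 20 weeks, whereas exposure starts six weeks before conception. Even then p is 0.043 and 0.0043. The first-rank Benjamini–Hochberg limit would be 0.05/15 = 0.0033 for the 15 primary outcomes in Table 2, or 0.05/23 = 0.0022 with the secondary ones. The family of tests is not defined, and other small p-values would relax that limit.

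A reader might also infer that later vaccination should be taken out of the main estimate. The stated aim is safety of vaccination during pregnancy, so that would change the question.

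**Conclusion.** The point holds as an inconsistency between section 3.5.1 and Appendix 1. For index dates after 20 weeks, the clean window excludes only hypertensive disease that already has a hospital record, so the claim that only incident cases are counted is not met for this outcome. No planned analysis shows how much this matters.

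The direction is toward the null if leakage is equal. It can be either way if uptake depends on existing hypertension, a possibility the protocol itself allows for pregnancy complications in general. Neither the size nor the direction can be derived from the documents. Under the illustrative assumptions the effect is modest: a true RR of 1.2 is seen as 1.19–1.16, and a null RR as about 1.05 at k = 1.5. These figures scale directly with the proportion of events that follow late vaccination. The finding calls for a correction and a check, and does not show that the main estimate is invalid.

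**What to change.** 1. Keep *Any* in Table 2 as the vaccination timing for the main analysis of hypertensive disorders.
2. Pre-specify, whether or not a signal is seen, a sensitivity analysis for this outcome restricted to women whose index vaccination was at or before 19+6 weeks, with their matched controls. By Table 2's own note every later case in that set is incident. Report it beside the main estimate.
3. Reword section 3.5.1 to say that, for hypertensive disorders and later vaccination, the clean window excludes only disease with a prior hospital record in the current pregnancy.

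The cost is one extra model on data already held, since gestational week at vaccination is already needed for matching, plus one changed sentence. The restricted analysis will have fewer women and a wider confidence interval. A difference from the main result may also reflect a true difference by timing of vaccination, so it should be read as a check on the main estimate and not as its replacement.
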